### Statistical Analysis Plan

**Power and Sample Size Considerations:** Power calculations were carried out based on our recently published study which measured NPY, at baseline and peak time-points, in response to a single cardiopulmonary exercise stress test (CPX). Achievement of a Cohen’s d effect size of .5 will suggest statistically and clinically significant effects of the treatment within the CP/PTSD group. Thus, in order to obtain a power of 80% at the 5% level of significance a sample size of 30 participants will be required.

**Data Analyses:** Baseline demographics and descriptive variables (e.g., age, gender, pain duration) will be summarized. Descriptive summaries for continuous variables will be presented in terms of means and standard deviations while discrete variables will be summarized in terms of relative frequencies and percentages.

**Aims 1-2 &4:** The hypotheses under Aims 1, 2 and 4 will be evaluated using unconditional latent growth models (LGMs). The approach does not assume a linear trajectory and is thus ideal for this proposal. The intercept of the LGM will be centered on the baseline self-report data (i.e., first slope loading will be fixed to 0.0). The intermittent time point (midpoint) will be freely estimated, and the final post-training time point will have a corresponding slope factor loading fixed to 1.0. Accordingly, the mean and variance of the slope factor will convey the fixed (average) and random effects (individual differences) of change across exercise training. Effects of the exercise program will be evidenced by a significant slope factor mean (indicating significant change in the metric of interest). A significant slope variance will indicate individual differences in change across training and support further investigation of predictors of the variability.

**Aim 3:** At both CPX testing time-points, the putative mechanisms under investigation (reward, self-regulation, exercise-based SE and IM) will be correlated with each other using Pearson or Spearman correlations, as appropriate. Based on these findings, these putative psychological mechanisms will be entered as predictors in a discriminant function analysis to predict exercise maintenance.

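### With 30 participants, the slope-variance test is too weak to decide whether NPY is examined as a predictor of change

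*Combined protocol and SAP*

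**What the plan says.** The Data Analyses paragraph for Aims 1-2 & 4 in the Statistical Analysis Plan specifies unconditional latent growth models over baseline, midpoint and post-training. The baseline loading on the slope is set at 0 and the post-training loading at 1. For the occasion between them the wording is: "The intermittent time point (midpoint) will be freely estimated". The plan then says that "the mean and variance of the slope factor will convey the fixed (average) and random effects (individual differences) of change across exercise training". A significant slope mean is the evidence of a training effect. For the variance it says: "A significant slope variance will indicate individual differences in change across training and support further investigation of predictors of the variability".

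The plan does not state whether residual variances are free or equal across occasions, whether intercept and slope covary, which test of the variance is used, what is done with improper solutions, or what follows if the variance is not significant. The power paragraph covers a mean change only: "in order to obtain a power of 80% at the 5% level of significance a sample size of 30 participants will be required".

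**The concern.** An unconditional model contains no predictors, so NPY is not in it. Hypotheses 1b, 2b and 4b are all about NPY correlating with change, and the plan gives no separate test for them. The only step leading from the growth model to predictors of change is a significant slope variance.

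A variance component is hard to estimate from three occasions on 30 people, and harder when the midpoint loading must be estimated too. If the test usually misses real differences between participants, the plan's wording would discourage the analyses the study was set up to do. Alternatively, those analyses would go ahead on the strength of an inadmissible fit. Because the residual structure is unstated, it could also be chosen after the data are seen, and that choice changes the result of the test.

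**Working it through.** **1. The plan's own figure.** Inputs from the power paragraph: d = 0.5, 80% power, 5% level. For a within-group mean change, n = ((1.96 + 0.842)/0.5)² = 31.4, so 32, and power at 30 is 78%. A paired t-test needs 34 two-sided (75% power at 30) or 27 one-sided. Thirty is about right for a mean change, but the calculation does not address a variance.

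**2. Counting.** Three occasions give 3 means + 6 variances and covariances = 9 moments.
- Free residual variances: 2 factor means + 2 factor variances + 1 covariance + 1 loading + 3 residuals = 9 parameters, df = 0.
- Equal residual variances: 2 + 2 + 1 + 1 + 1 = 7 parameters, df = 2.

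Both counts assume an intercept-slope covariance, which the plan does not mention.

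**3. Where the weakness comes from.** Let m1, m2, m3 be the sample means and s12, s13, s23 the covariances. With free residuals the solution is closed-form:
- midpoint loading λ = (m2 − m1)/(m3 − m1)
- slope variance = (s23 − s13)/λ − (s13 − s12)/(1 − λ)

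The loading is identified only through the mean change, and both λ and 1 − λ are divisors. If mean change is near zero, or λ is near 0 or 1, the estimate is unstable. With equal residuals, 6 variances and covariances cover 5 covariance parameters (3 factor, 1 loading, 1 residual), so the loading no longer depends on the means alone.

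**4. Simulation at n = 30.** The documents give no variance components, so these are assumptions: intercept variance 0.8, intercept-slope covariance −0.1, true λ = 0.5, and mean change equal to half the SD of change, √(slope variance + 2 × residual variance). Significance is Wald z > 1.96. Free-residual columns: 20,000 replicates, closed form with delta-method standard errors. Equal-residual column: 400 replicates, numerical maximum likelihood, Monte Carlo error up to about 5 points. Improper means at least one negative variance.

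| Slope var. | Residual var. | Ratio | Free: improper | Free: significant | Free: significant, no negative variance | Equal: significant |
|---|---|---|---|---|---|---|
| 0.3 | 0.1 | 3 | 66% | 9% | 0.5% | 64% |
| 0.3 | 0.2 | 1.5 | 66% | 5% | 0.3% | 29% |
| 0.3 | 0.3 | 1 | 66% | 4% | 0.3% | 19% |
| 0.6 | 0.1 | 6 | 63% | 24% | 4% | 95% |
| 0.6 | 0.2 | 3 | 59% | 12% | 2% | 64% |
| 0.6 | 0.3 | 2 | 59% | 8% | 1% | 41% |

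With free residuals the slope variance itself is negative in 8–33% of samples. With equal residuals, repeat runs put the test at 16–69% for ratios of 1 to 3. At a ratio of 5 (0.5 against 0.1 with a larger mean change, or 1.0 against 0.2) it reaches 90%.

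**5. A likelihood-ratio test does not remove the problem.** The plan names no test. A 2-df likelihood-ratio test with residual variance 0.2 is significant, free / equal residuals, in 7% / 12% at slope variance 0.10, 18% / 31% at 0.25, 30% / 67% at 0.60 and 54% / 92% at 1.0.

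**6. What the preliminary data can say.** Treat the reported p-values as paired t-tests with n = 5 (an assumption).
- BDI-II: the change of 11.4 with p = 0.05 gives an SD of change of 11.4/2.776 × √5 = 9.18. Its variance is (9.18/15.4)² = 0.36 of baseline variance.
- CAPS-5: the change of 16.6 with p = 0.10 gives 16.6/2.132 × √5 = 17.41, and (17.41/10.2)² = 2.9.

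These are variances of observed change and include residual error. They differ eightfold, so the documents do not show where in the range the true slope variance lies.

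**The case against.** A reader might infer that the model has zero degrees of freedom and that its variance test is therefore unusable. The documents do not support that. Zero df depends on free residual variances, which the plan does not state. Even then a saturated model still estimates and tests the slope variance; what is lost is the overall fit test. Nor is the test always weak. With free residuals, Wald significance reaches about 83% at a slope variance of 2.5 with residual variance 0.1, and with equal residuals it is about 90% or more once slope variance is five times residual variance.

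A reader might also take the sentence as a formal gate that closes the NPY analyses. The plan speaks of support, gives no stopping rule, and states hypotheses 1b, 2b and 4b without condition. Hypotheses 1a, 2a and 4a are baseline correlations and need no slope variance.

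These objections limit the claim but leave two facts. No other criterion for examining predictors of change is given, and the test offered is weak over a plausible range. Frequent improper fits also stand if residuals are free: they stayed above half at every slope variance tried, including 61% at a slope variance of 2.56.

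**Conclusion.** The point holds in limited form. At n = 30 the slope-variance test should not decide whether NPY is examined as a predictor of change, and a non-significant result is not evidence that participants changed alike.

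Under the assumed variances and d = 0.5, free residuals give about 60–65% improper fits and significance in roughly 3–24%. Equal residuals raise this to about 16–69% for slope-to-residual variance ratios of 1 to 3, and to 90% or more from a ratio of 5. That includes the most favourable corner of the assumed range, slope variance 0.6 with residual variance 0.1. All these sizes rest on variance components the documents do not supply. The parameter count and the missing specification do not depend on them.

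**What to change.** In the Aims 1-2 & 4 paragraph:
- Remove slope-variance significance as the condition for examining predictors.
- Pre-specify each NPY-change association in hypotheses 1b, 2b and 4b, and estimate it with a confidence interval whatever the variance test shows.
- Report the slope variance with its interval, as description only.
- Hold residual variances equal across occasions, keep the midpoint loading free, and state how improper solutions will be handled.
- Take mean change from the baseline-to-post contrast.

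The cost is SAP wording. Equal residual variances are an added assumption, a small downside. They do not rescue the test at moderate slope variances, so the second item does the main work. With 30 participants a correlation of 0.5 is detected with about 81% power and one of 0.3 with about 36%, so the intervals should carry the interpretation.

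Two further changes may look attractive but should not be made. Fixing the midpoint loading at 0.5 would impose the linear course the plan sets out to avoid, and the Exercise Prescription raises intensity up to week 6 and then holds it. Adding the 1- and 3-month follow-ups to the same slope factor would mix change during training with maintenance after it.

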## Protection of Human Subjects

### 8.1. Risk to Subjects

#### 8.1a. Human Subjects Involvement and Characteristics

The study aims to consent and enroll ~90 participants (half male, half female) aged 18-60 in the screening evaluation in order to enroll 30 participants into the experimental study procedures (cardiopulmonary exercise testing, and training) over the full 2 years of the grant. Participants in the proposed research project will be include veterans and non-veterans, women and men who are between 18 and 65 years of age, of ethnic and racial backgrounds in proportion to those of the larger Boston community.

##### *Inclusion/Exclusion Criteria*

Participants will be included only after participation in the informed consent process and agreeing to the study procedures as approved by the Institutional Review Boards of both Boston University School of Medicine and VA Boston Healthcare System (where the study will be conducted). An IRB approved HIPAA waiver will be obtained in order to conduct telephone pre-screening of potential participants before scheduling them for in-person screening evaluations.

Participants with posttraumatic stress disorder (PTSD) and chronic pain (CP/PTSD) will be included in this study only if a medical history, physical examination, vital signs, EKG, and baseline laboratory studies including urine toxicology screens and a negative urine pregnancy test (woman only) indicate that symptom-limited cardiopulmonary exercise stress (CPX) testing will be safe. Women of child bearing capacity must agree to use effective contraception while participating; a urine pregnancy test performed on the morning prior to completing CPX testing will also be done.

Participants entering the study will be relatively sedentary, as defined by the American College of Sports Medicine (i.e., performing less than 30 minutes/day and less than 150 minutes per week of moderate physical activity). Participants must be free of medications and other substances (e.g., illicit drugs and alcohol) with effects that could hinder data interpretation for 2-6 weeks before the cold pressor test (CPT) and CPX testing depending on the medication and frequency of use (which must be cleared by the study Co-I and study MD, [name]). Psychotropic medications are allowed, however, as long as the participant has been stable on them for three months. Those using tobacco will be included in the study and will not be required to lower or stop their dosage/intake; intensity of smoking will be monitored across the study via use of urine testing for cotinine (a long-lived metabolite of nicotine) at each test session. Regular morning nicotine users will be instructed to smoke/chew to satisfaction just prior to arriving at the Clinical Studies Unit for testing, which will be approximately 2-3 hours prior to performance of the CPT and CPX. If using pain medications other than opiates (which will not be allowed) participants must be off of them for 5 half-lives before CPT/CPX testing, generally about 24 hours.

Participants must have an ICD-9 diagnosis of chronic pain with a musculoskeletal etiology, as confirmed by the rehabilitation medicine doctor consulting to the study, and a confirmed comorbid psychiatric diagnosis of PTSD. More specifically, the CP/PTSD participant must meet for current chronic PTSD ( $\geq 3$  months) as assessed by the CAPS-5, 1-Month Diagnostic Version. As we are interested in NPY system functional status as correlated with putative mechanisms that predict exercise maintenance (self-regulation, reward sensitivity, self-efficacy and intrinsic motivation for exercise), as well as exercise training related changes in clinical symptoms (pain-related interference and sensitivity, depression and PTSD severity), there will be no lower limit "cut-off score" for entry into the study, as long as DSM-5/CAPS-5 criteria are met. The literature suggests that there are relationships between PTSD severity and deficits in NPY. Therefore, in order to have optimum power to investigate *correlations* between NPY and these dependent variables, it is important to have the broadest possible range of NPY levels. Other anxiety or depressive disorders are permitted. Participants may be involved in supportive psychotherapies as long as their participation has been stable for 3 months prior to study entry and remains stable throughout the course of the study. Also, any participant with a mild TBI, grades I-III, as determined by the BAT-L, will be included. These rigorous criteria are being employed for safety reasons, as well as to allow valid and meaningful interpretation of the study results in this mechanism-focused study. These are procedures we already routinely use.

Participants will be excluded from participation in the study if they have a life threatening or acute physical illness (e.g., cancer), current schizopreniform illnesses (except for psychosis NOS due to PTSD

related sensory hallucinations), bipolar I disorder, or active suicidal or homicidal ideation or other risk to self or others requiring clinical intervention. Individuals with current or past alcohol and/or substance dependence (less than three months from date of screening assessment) will be excluded. Women who are pregnant or are planning to become pregnant within the next six months will also be excluded. Individuals seeking significant new pain treatment such as surgical interventions or who have a neuropathic origin to their pain will be excluded. Participants with chronic pain who cannot tolerate exercising in an upright bike and those who have had a clinical history of coronary artery disease or positive stress test, uncontrolled cardiac arrhythmia, a QTc greater than 500, moderate-to-severe aortic stenosis, > moderately severe arterial hypertension (systolic > 165 mmHg, diastolic >100 mm Hg) and more than first degree atrioventricular block also will be excluded from participation. Individuals with moderate to severe TBI, as evidenced on the BATL, will not be included in the study and will be referred for appropriate care through the VA TBI center of excellence at VABHS or an appropriate VA or Boston community clinic. Finally, individuals taking chronic medications (e.g., medication for high blood pressure, high cholesterol, glucose intolerance or diabetes) will be excluded. As noted above, psychotropic medications will not be excluded due to their common usage in the CP/PTSD population.

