**Hypothesis 1b:** Changes in resting plasma NPY levels and the release of NPY in response to standardized cardiopulmonary exercise testing (CPX) conducted before and after a 3-month progressive exercise-training program will correlate with improvements in self-regulation and reward sensitivity.

**Aim 2.** Evaluate whether changes in NPY correlate with changes in self-efficacy and intrinsic motivation for exercise in response to a rigorous 3-month individually tailored, exercise-training program.

**Hypothesis 2a:** At baseline, acute exercise-induced increases in plasma NPY during CPX will correlate with exercise-related self-efficacy and intrinsic motivation to exercise.

**Hypothesis 2b:** The release of NPY during CPX will increase in response to the 3-month exercise-training program and correlate with increases in self-efficacy and intrinsic motivation to exercise.

**Aim 3.** Determine whether capacities for self-regulation and reward sensitivity, as well as self-efficacy and intrinsic motivation for exercise change in response to the 3-month exercise-training program and predict exercise maintenance.

**Hypothesis 3:** At endpoint, the factors under investigation will significantly predict exercise maintenance.

**Aim 4.** Evaluate whether changes in NPY system function across the 3-month exercise-training program correlate with improvements in pain sensitivity and interference, as well as depressive and PTSD symptoms.

**Hypothesis 4a:** At baseline, CPX-induced increases in plasma NPY will not correlate with pain-related interference and sensitivity, depression or PTSD severity.

**Hypothesis 4b:** At endpoint, CPX-induced increases in plasma NPY will correlate with reductions in pain-related interference and sensitivity, as well as with reductions in depression and PTSD symptoms.

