**Cold Pressor Test (CPT):** Per standard CPT procedures, participants will hold their right hand, up to the wrist, in a temperature controlled ice water bath, while keeping the hand still. They are instructed to say when they first experience pain and to withdraw their hand when the pain becomes intolerable. Pain threshold is defined as the number of seconds between hand immersion and the first report of "pain." Pain tolerance is defined as the number of seconds between hand immersion and hand withdrawal from the water. To prevent risk to subjects, a 7-minute time limit for immersion, unknown to the patient, is imposed. The CPT is performed just before and 30' after CPX testing to assess effects of acute exercise on pain sensitivity. To assess effects of exercise training on resting pain sensitivity, the CPT also will be performed 1-

2 days before each CPX and at the exercise-training midpoint. At these sessions, participants will engage in the same procedures (except the CPX) at the same time of day as those performed at the CPX sessions.

**Progressive Exercise Training Program:** After the initial CPX and CPT sessions, participants return to the CSU for 2 exercise-training sessions with our exercise physiologist. A pre-programmed heart rate monitor that “beeps” when exercise intensity increases is provided to participants to ensure that the targeted HRR is reached in accordance with individualized progressive exercise prescriptions. After these sessions, the exercise physiologist will instruct participants to gradually increase the frequency of their prescribed exercise sessions at home (per protocol) to 3x/week by week 4. During weeks 4, 7, and 10 an investigator will call participants to check-in and discuss any barriers to exercise. Basic motivational interviewing techniques (i.e. reflective listening) and problem solving strategies (the current standard of care in this area) will be used to facilitate exercise compliance while maintaining safety. To verify home exercise, participants will wear an actigraph and heart rate monitor that measures activity and heart rate. Data from the heart rate monitor will be downloaded and reviewed with participants upon return to the clinic for test sessions.

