**Exercise Prescription:** The exercise prescription entails a 10 minute warm-up and cool down at 30-50% HRR. The exercise portion lasts 30 minutes, initially at 40-60% HRR during weeks 1-2 followed by incremental increases in the HRR range by 10% every two weeks through week 6 (midpoint) when the exercise intensity is increased to 70-80% HRR and held there during weeks 7-12.

**Exercise Training Follow-Up:** Phone calls will be made at 1- and 3-months follow-up after completion of exercise training and testing. Ratings will be administered to determine whether exercise and improvements in symptoms and motivation have been sustained, as well as to identify barriers to continued exercise.

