**7. Potential coercion:** We expect that any risks of coercion will be low. First, participants who do not wish to participate in the study or who wish to drop out of the study after enrollment will not experience any negative consequences and will be referred to VA or community-based treatment for CP/PTSD if desired. Second, potential participants will initiate contact with study staff if they are interested, which reduces coercion. A potential human subjects concern is whether the financial compensation offered is too high and therefore coercive to participants. We believe the rate of compensation for the current study is fair and matched to time needed to complete procedures and any additional inconveniences. Travel is compensated to address a potential disincentive to study participation. Participants will be compensated for most study sessions based on the time required—as payment may be needed to offset babysitting costs or time away from work. We plan to pay at rates commensurate with time spent (~\$20 an hour), which is the standard at VABHS. Specifically, participants will be compensated \$90 for participation in the full screening evaluation, \$50 for participation in each CPT session (3 total), \$50 for participation in each CPX testing session (2 total), \$25 for in clinic exercise training sessions (up to 10 total) and \$10 for each home exercise session (26-31 total), \$5.00 for each telephone call (during weeks 3 through 12 while he/she is exercising at home (up to 10 total)), and \$20 for each follow-up phone call (1-month and 3-month). If the participant participates in all of the study procedures over the ~6 month study, he/she will be compensated up to \$990.00. Finally, all study procedures will be fully explained during the informed consent process such that participants can make an informed decision regarding their level of commitment and willingness to engage in study procedures given the risks. In addition, participants will be informed and reminded that they are free to withdraw from the study at any point without forfeiting payment for any procedures in which they have already participated.

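### Aim 3 predicts exercise maintenance without using the baseline stage-of-change measure, so activity that predates the programme cannot be separated from maintenance gained through it

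*Combined protocol and SAP*

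**What the plan says.** **Entry.** The Inclusion/Exclusion Criteria describe entrants as relatively sedentary, meaning "performing less than 30 minutes/day and less than 150 minutes per week of moderate physical activity". No criterion refers to stage of exercise behaviour.

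**Programme.** Under Exercise Prescription, "The exercise prescription entails a 10 minute warm-up and cool down at 30-50% HRR". Then: "The exercise portion lasts 30 minutes, initially at 40-60% HRR during weeks 1-2". Later "the exercise intensity is increased to 70-80% HRR and held there during weeks 7-12". Under Progressive Exercise Training Program, participants "gradually increase the frequency of their prescribed exercise sessions at home (per protocol) to 3x/week by week 4".

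**Stage measure.** The Measures table in APPROACH schedules TTM stage at screening, baseline CPX, midpoint, post-training CPX and the follow-up calls. The instrument is described as continuous, and its categories include action and maintenance.

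**Aim 3.** Hypothesis 3 reads: "At endpoint, the factors under investigation will significantly predict exercise maintenance". The analysis first correlates reward, self-regulation, exercise self-efficacy and intrinsic motivation with one another. Then "these putative psychological mechanisms will be entered as predictors in a discriminant function analysis to predict exercise maintenance". Neither baseline stage nor prior activity appears as a predictor, covariate or restriction.

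**The concern.** Aim 3 is meant to show that capacities which change with training go on to predict maintenance. The study has one group, so no comparison arm separates an acquired habit from an existing one. If some participants already exercise at entry, they may score higher on self-efficacy and motivation and may also be more likely to be exercising at follow-up. Baseline stage would then drive both sides of the association, and the analysis would credit the training mechanisms with part of a habit that came before them.

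The protocol itself gives a reason to expect such a link. Section C of SIGNIFICANCE reports higher exercise self-efficacy in the action and maintenance stages than in the earlier ones, and self-efficacy is one of the Aim 3 predictors.

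**Working it through.** **1. The plan's own figure.** The documents give no sample-size or precision figure for Aim 3. The only one is n = 30 for a within-group d of 0.5 (80% power, 5% level). The two-sided normal approximation gives ((1.960 + 0.842)/0.5)^2 = 31.4, or 32, close to 30. Nothing below depends on it.

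**2. Weekly minutes.**
- Entry ceiling: 29 min x 5 days = 145, or 21 min x 7 days = 147. Both are eligible.
- Exercise portion at full frequency: 3 x 30 = 90 min/week. Ratio: 145/90 = 1.6.
- Whole session, warm-up and cool-down 10 minutes in total: 3 x 40 = 120 min/week, still under the ceiling.
- Whole session, 10 minutes each: 3 x 50 = 150 min/week, which no eligible person can exceed.
- Cross-check from the payment schedule, "for each home exercise session (26-31 total": 26 x 30/12 = 65 to 31 x 30/12 = 78 min/week of exercise portion over 12 weeks, leaving out clinic sessions.

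So the entry rule admits people with some existing activity, up to more minutes than the exercise portion. Whether it admits more than the full session time depends on how the warm-up sentence is read.

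**3. The stage gap in self-efficacy (SIGNIFICANCE, section C).**
- Means and SDs: 51.4 (9.45) active, 38.64 (7.15) non-active. With equal groups, d = 12.76 / sqrt((9.45^2 + 7.15^2)/2) = 12.76/8.38 = 1.52.
- The same sentence gives F(1,16) = 2.02, p = .17 and eta-squared .11. The F and eta-squared agree: 2.02/(2.02 + 16) = 0.11. With 9 per group they imply d = sqrt(2.02 x (1/9 + 1/9)) = 0.67.
- In reverse, d = 1.52 with 9 per group gives F = 1.52^2 x 4.5 = 10.4. Over all splits of 18 with at least 2 per group, the means and SDs give an unadjusted F of 3.3 to 10.7, never 2.02.

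The reported gap is therefore internally inconsistent and cannot size the bias.

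**4. What omission could do, under assumptions.** A simulation used n = 30 and 20,000 runs per scenario, with one predictor tested at two-sided 5% and no true effect of self-efficacy on maintenance within stage. Three inputs are assumed: the share active at entry, the maintenance rates, and a stage gap that is still present at endpoint. The gap is taken either in full (12.76 points) or halved (6.38 points, d = 6.38/8.38 = 0.76, near the 0.67 above).

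| Active at entry | Maintenance, active vs not | Stage omitted, full gap | Stage omitted, half gap | Stage included |
|---|---|---|---|---|
| 10% (3) | 80% vs 40% | 8.6% | 6.1% | 4.7-4.9% |
| 10% (3) | 90% vs 30% | 14.9% | 8.0% | 4.5-4.8% |
| 20% (6) | 80% vs 40% | 15.3% | 7.9% | 4.6-4.7% |
| 20% (6) | 90% vs 30% | 31.0% | 12.9% | 4.2-4.3% |
| 30% (9) | 80% vs 40% | 21.9% | 10.0% | 4.3-4.6% |
| 30% (9) | 90% vs 30% | 45.6% | 17.3% | 3.9-4.0% |

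Entries are false-positive rates. Including stage brings them to about the nominal level in every scenario.

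**The case against.** The strongest reply is that the entry rule does its job. It is stated as a professional body's definition of sedentary. It limits moderate activity of any kind, which is not structured exercise, while the prescription is heart-rate targeted and rises in intensity. The documents give no rule for assigning stage, so nothing shows that a person under the limit would be classed as action or maintenance. The predictors are taken at endpoint, after every participant has had 12 weeks of prescribed exercise, and no passage shows that a baseline gap lasts that long. The self-efficacy comparison is small, non-significant, and comes from women with fibromyalgia.

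All of this stands, and it rules out two inferences that a reader might draw. The first is that entrants may already exceed what the programme prescribes. This holds in minutes for the 90-minute exercise portion. It fails for the full session if warm-up and cool-down are 10 minutes each, and minutes are not dose. The second is that a gap of about 1.5 SD measures the bias. The test statistic in the same sentence contradicts it.

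What the reply does not remove is the omission itself. No criterion keeps out people in an active stage, the measure that would identify them is collected, and Aim 3 does not use it. The plan also names no instrument, cut-off or time point for maintenance, so nothing in the outcome separates continued from newly acquired exercise.

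**Conclusion.** The point holds as a gap in the Aim 3 analysis. Endpoint self-efficacy or motivation could be associated with maintenance partly because both reflect activity that predates the programme, and the planned discriminant analysis cannot tell the difference.

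The size cannot be determined from the documents. The 6% to 46% range rests on an assumed 10% to 30% active at entry, assumed maintenance rates, and persistence of the gap to endpoint. With the half gap, which is closer to the reported F, the range is 6% to 17%. The lower end is nearly harmless. If nobody enters in an active stage, the confounding shown in this simulation does not arise, and reporting the count would show that. It would be wrong to say that prior exercisers will be counted as maintainers: the documents make this possible, not demonstrated. One aim is affected, and the remedy is an inexpensive improvement.

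**What to change.** Add to the Aim 3 paragraph of the Statistical Analysis Plan:

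- Enter the baseline TTM stage measure first in the discriminant analysis, then the psychological scores, and report what the scores add beyond it. If few participants are in an active stage, use the continuous score, so that the term stays estimable.
- Report how many participants were in an active stage (action or maintenance) at screening.
- Repeat the analysis in those non-active at screening, as a sensitivity analysis only. On the assumed 10% to 30% it would drop 3 to 9 of 30 and leave 27 to 21, too few to carry the main result with at least four constructs as predictors.

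The cost is a few sentences, no new data, about one degree of freedom at n = 30, and possibly less favourable reported discrimination. The entry limit, exercise prescription and sample size do not change.
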